### 2.2 Subjective Assessment

Given the significant QOL impact of nasal obstruction, it is important to measure not only the physical symptoms (congestion, obstruction and ability to breathe) but also the impact of those symptoms on the patient's ability to sleep and the related consequences on rest, productivity, concentration and ability to participate in the normal daily activities of work and life.

In addition to the physical benefits of increased nasal patency, there are significant quality of life benefits that are associated with better breathing. After correcting nasal obstruction patients report significantly better sleep function (e.g. better night's sleep; lessened waking up during the night and difficulty falling asleep) as well as better psychological function (e.g. concentration, productivity and frustration). (Brown, Hopkins, et. al). We believe that these benefits may well be durable beyond the initial six months of the study in terms of sustained quality of life impact.

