### 2.3 Study Design and Objectives

This is a prospective, non-randomized, multicenter follow-up study to collect long term data on a cohort of patients who participated in the Aerin Medical TP 258 study, “A Prospective, Multi-Center, Non-Randomized Study to Evaluate Treatment of Nasal Airway Obstruction Using the Aerin Medical Device.” The study will be conducted in a maximum of 8 centers. Follow-up data will be collected at the 12, 18 and 24-month post-procedure timepoints for all patients who have completed the above-mentioned study. The objective of the study is to evaluate the long-term durability of benefits associated with the Vivaer Stylus procedure.

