## 1 INTRODUCTION

Aerin Medical believes that the benefits demonstrated with the Vivaer Stylus procedure in the Aerin Medical TP258 study, “A Prospective, Multi-Center, Non-Randomized Study to Evaluate Treatment of Nasal Airway Obstruction Using the Aerin Medical Device” may be durable beyond the initial six months of the study in terms of sustained quality of life impact. The TP258 study demonstrated the safety and effectiveness of the treatment procedure to the 26-week endpoint and was the clinical basis for 510(k) clearance of the device by the FDA (K172529 5 December 2017). This prospective follow-up study on a cohort of subjects from the TP258 study collected nasal obstruction symptom evaluations (NOSE) and responses to an Aerin Medical Quality of Life survey at 12, 18 and 24 months after the procedure.

The purpose of this statistical analysis plan is to outline the necessary statistical techniques required to evaluate the efficacy outcome parameters in the Final Report for Clinical Protocol (TP465).

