## 2 OBJECTIVE

The objective of the study was to evaluate the long-term durability of benefits associated with the treatment procedure using the Vivaer Stylus for relief from nasal airway obstruction.

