## 3 STUDY DESIGN

### 3.1 Overview

This investigation was a prospective extended follow-up study of subjects who had participated in the TP258 multicenter trial to evaluate the safety and efficacy of the Vivaer Stylus. Subjects were followed to the 26-week endpoint in that study. Subjects agreeing to participate in this follow-up study were to provide self-evaluation NOSE and quality of life measures at 12, 18, and 24 months after the treatment procedure. There was no concurrent control population or blinding in either the original TP258 study or in this extended follow-up study.

Self-administered evaluations were scheduled for 12, 18, and 24 months after the treatment procedure. Evaluations could occur in person with study personnel, by phone, or by mail.

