### 3.2 Population and Sample Size

Subjects who completed participation in the Aerin Medical TP258 study, “A Prospective, Multi-Center, Non-Randomized Study to Evaluate Treatment of Nasal Airway Obstruction Using the Aerin Medical Device” were eligible for inclusion and participation in this study. These subjects had exhibited significant symptoms of nasal obstruction attributed to internal nasal valve dysfunction prior to undergoing treatment with the Aerin Medical Vivaer Stylus and completing 26 weeks of follow-up in the Aerin Medical TP258 study.

The maximum sample size for this extended follow-up of the TP258 study was 49 subjects, the number that completed the TP258 study.

All eligible subjects who provided informed consent and completed at least 1 survey were included in the analysis population. A second nonenrolled population was defined as those subjects enrolled in the TP258 study that chose not to enroll in this extended follow-up study. The purpose of the nonenrolled population was to allow comparison of characteristics of subjects who self-selected to enroll in the follow-up study with those who chose not to enroll in the follow-up study.

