## 4 OUTCOME MEASURES

### 4.1 Nasal Obstruction Symptom Evaluation (NOSE)

Nasal valve evaluation is based on clinical observations of signs and symptoms with no easily obtained, reproducible objective measurement techniques of the valve; therefore, the Nasal Obstruction Symptom Evaluation (NOSE) questionnaire was used in the TP258 study as the primary outcome measure and was continued in this follow-up study. The NOSE questionnaire is a validated disease-specific health status instrument used by clinicians to measure the outcome of subjects treated for nasal obstruction. The NOSE survey consists of 5 items, each scored using a 5-point (0 - 4) Likert scale. The 5 item scores are summed and then multiplied by 5 to make a total score range of 0 through 100, where higher scores indicate worse obstruction. Severity of symptoms can be classified as mild (range, 5-25), moderate (range, 30-50), severe (range, 55-75), or extreme (range, 80-100) nasal obstruction, based on responses to the NOSE survey.

Treatment responders were defined in the TP258 study as subjects achieving a 15 point or greater improvement in the NOSE score compared to baseline.

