### 5.7 Primary Analysis

Mean NOSE scores at baseline and each follow-up evaluation will be calculated to show the time course progression of improvement. Repeated measures analysis of variance (ANOVA) will be used to test for differences from baseline to follow-up evaluations. The statistical significance level will be set at 5% (p-value < 0.05).

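### The aim is durability past six months, but the primary NOSE test compares with pre-procedure baseline and nothing estimates change since week 26

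*SAP*

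**What the plan says.** Both documents give the same aim. Protocol section 2.3: "The objective of the study is to evaluate the long-term durability of benefits associated with the Vivaer Stylus procedure". SAP section 2: "The objective of the study was to evaluate the long-term durability of benefits associated with the treatment procedure".

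The objective sentences set no reference time, but the introductory text of both documents does. Protocol section 2.2 expresses the belief that "these benefits may well be durable beyond the initial six months of the study", and SAP section 1 says that the benefits "may be durable beyond the initial six months of the study". SAP section 1 also treats safety and effectiveness up to week 26 as already established by TP258.

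For the primary analysis, SAP section 5.7 plans NOSE means by visit and one test: "Repeated measures analysis of variance (ANOVA) will be used to test for differences from baseline to follow-up evaluations". The opening of SAP section 5 makes the pre-procedure state the reference for each subject. In section 5.8, the responder proportion (an improvement of at least 15 points) and the mean percent improvement are also measured from baseline. Severity categories and item responses are tabulated by visit.

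A week-26 NOSE score should exist for these subjects. SAP section 3.1 states "Subjects were followed to the 26-week endpoint in that study", and SAP section 4.1 says that NOSE "was used in the TP258 study as the primary outcome measure and was continued in this follow-up study".

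**The concern.** If benefit up to week 26 is taken as shown, what this study adds is what happened afterwards. A difference from pre-procedure baseline is compatible with a benefit fully kept and with one that has mostly gone. The 15-point responder measure has the same limit: a subject whose improvement falls from 50 points to 15 still counts as a responder.

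There is no control group, so each subject's own course after week 26 is the only direct evidence on durability. As planned, a durability statement would rest on comparing visit means by eye, with no measure of uncertainty. It is not even certain that the week-26 mean will be among them, because section 5.7 does not say whether its follow-up evaluations include the TP258 visits.

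**Working it through.** **Is the contrast specified anywhere?** SAP sections 5 to 5.9 were read for any change since week 26, any durability criterion and any confidence interval. None appears. Section 5.8 names t-tests and ANOVA only in general terms. The quality-of-life items ask about change since before the procedure, so they do not fill the gap.

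**Inputs.** The documents state no power, SD, effect size or margin, so there is no planned figure to reproduce. They do give:

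- the 5% significance level (section 5.7; two-sided is assumed)
- the three follow-up times
- the ceiling on numbers (section 3.2): "The maximum sample size for this extended follow-up of the TP258 study was 49 subjects, the number that completed the TP258 study"

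Everything else is an assumption: 40 to 49 subjects analysed, an SD of change from baseline of 20 to 30 points, an SD of change from week 26 of 15 to 25 points, and week-26 benefits of 15, 20 or 30 points.

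**Step 1: smallest significant improvement over baseline.** The repeated-measures ANOVA is taken with four time points (baseline, 12, 18 and 24 months), compound symmetry and pooled error df = 3(n − 1). The critical mean is t(0.975, df) × SD/√n. For n = 40 and SD 20, this is 1.980 × 20/√40 = 6.26. Power is from the noncentral t distribution.

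| n | SD | Critical mean | Power, 15 points left (half of 30) | Power, 10 points left (half of 20) |
|---|---|---|---|---|
| 40 | 20 | 6.26 | 0.997 | 0.880 |
| 40 | 25 | 7.83 | 0.964 | 0.709 |
| 40 | 30 | 9.39 | 0.880 | 0.552 |
| 49 | 20 | 5.65 | 0.999 | 0.935 |
| 49 | 25 | 7.06 | 0.987 | 0.794 |
| 49 | 30 | 8.47 | 0.935 | 0.640 |

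A simple paired t-test changes little: critical means are 5.74 to 9.59, and power with 15 points left is 0.87 to 0.999. With a Bonferroni adjustment for three visits and pooled error, that power is 0.77 to 0.997.

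**Step 2: how much loss still gives p < 0.05?** With an observed improvement at the critical mean, the share lost is 1 − critical mean/benefit.

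- 30-point benefit: from 1 − 9.39/30 = 69% to 1 − 5.65/30 = 81%.
- 15-point benefit: half-loss leaves 7.5 points. That exceeds the critical mean at SD 20 (both n) and at SD 25 with n = 49, so in three of the six cells. By paired t, the largest compatible loss is 57/47/36% at n = 40 and 62/52/43% at n = 49 (SD 20/25/30).

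**Step 3: what would the missing contrast deliver?** The 95% half-width for mean change since week 26 is t(0.975, n − 1) × SD/√n. For n = 40 and SD 20, this is 2.023 × 20/√40 = 6.4 points. The range is 4.3 (n = 49, SD 15) to 8.0 (n = 40, SD 25). At n = 40, the interval would exclude zero with these probabilities:

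| True worsening since week 26 | SD 15 | SD 20 | SD 25 |
|---|---|---|---|
| 10 points | 0.98 | 0.87 | 0.69 |
| 5 points | 0.54 | 0.34 | 0.23 |

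**Step 4: can self-selection distort it?** Suppose the 40 of 49 completers with the best week-26 scores enrol and nothing truly changes. Their mean lies 0.318 SD better than that of all completers, so the expected apparent worsening is 0.318 × SD × (1 − r), where r is the correlation between the week-26 and follow-up scores. With a NOSE SD of 20 to 25 and r of 0.7 to 0.4, this runs from 0.318 × 20 × 0.3 = 1.9 to 0.318 × 25 × 0.6 = 4.8 points. If the selection score correlates only 0.5 with week-26 NOSE, it halves to about 1.0 to 2.4 points.

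**The case against.** The strongest reply is that benefit means improvement over the untreated state. TP258 defined response that way, and asking whether the improvement is still there at 12 to 24 months is an ordinary reading of durability. The objective sentences name no week-26 reference. The six-month wording is a stated belief in the introductory text, and there it concerns sustained quality of life. The plan also does not rest on a p-value alone: visit means, responder rates and severity categories would show marked waning. Near-complete loss would often fail the test as well: with 7.5 points left of 30, power is only 0.35 to 0.74. Finally, the added contrast is weak for small changes and is exposed to selective enrolment.

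Much of this stands. It is why the baseline contrast should stay and why the added estimate would not be a decisive test. It does not close the gap. Visit means carry no uncertainty for a within-subject change, and week 26 may not be among them. An observed result that has lost 69 to 81% of a 30-point benefit can still reach significance. Limited precision is a reason to show an interval, not to leave the change unestimated.

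**Conclusion.** The concern holds. The planned test is valid for whether some benefit remains, but nothing in the plan measures how much of the week-26 benefit was retained, which is central to the stated aim. Under the assumed inputs, a significant primary result is likely even after half of a 30-point benefit is lost (probability 0.88 to 0.999). It is moderately to very likely for a 20-point benefit (0.55 to 0.94). For a 15-point benefit the point is weaker, since half-loss is compatible with significance in only three of six cells.

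The absence of a week-26 contrast is a matter of reading and needs no assumption. The numbers rest wholly on assumed n, SDs, correlations and benefits. This should be fixed; it does not invalidate the baseline comparison.

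**What to change.** In SAP section 5.7:

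- Keep the baseline contrast and report it by visit.
- Add the within-subject change in NOSE from TP258 week 26 to months 12, 18 and 24, with 95% confidence intervals, in subjects with both scores and with n stated.
- Report the share of week-26 responders still responding at each visit.
- State that week 26 is part of the time course.
- Say that durability will be interpreted from both contrasts together, and that a non-significant change since week 26 is not proof of durability.

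In sections 5.1 and 5.6, extend the comparison of enrolled and non-enrolled subjects to week-26 NOSE, and note that selective enrolment of good responders could exaggerate worsening. Naming month 24 as the main time point would help but is optional.

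The cost is one contrast and some wording, with no new visits. The week-26 scores must be linked in if they are not already in the dataset; section 5.6 mentions only demographic and baseline data as available from TP258. The conclusion may become less favourable. SAP sections 1 and 3.1 describe the study in the past tense, so the contrast should be labelled post hoc if data had been seen before it was added.

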### 5.8 Secondary Analyses

Appropriate statistical techniques such as Student's t-test and ANOVA will be used for continuous outcome measures. Categorical and binomial outcomes will be examined using Fisher's exact test,  $\chi^2$ , or binomial tests. All analyses of secondary outcomes measures are exploratory for informational purposes only. No adjustments for multiple comparisons will be applied.

#### Nasal Obstruction Symptom Evaluation (NOSE)

The number and proportion (percent) of treatment responders ( $\geq 15$ -point improvement (decrease) in NOSE score from baseline to each follow-up visit) will be calculated.

Mean percent improvement from baseline to each follow-up evaluation will be calculated.

NOSE scores will also be summarized as number of subjects and percentage falling in each category (mild, moderate, severe, extreme) at baseline and each follow-up evaluation.

Responses to individual questions of the NOSE will be summarized as number of subjects and percentage falling in each response category (Not a Problem, Very Mild Problem, Moderate problem, Fairly Bad Problem, Severe problem) at baseline and each follow-up evaluation.

#### Aerin Medical Quality of Life Survey

The number and percent distribution of responses for each of the 21 items will be presented.

### 5.9 Data Pooling

Data from the investigational sites will be pooled for the primary analysis but may be examined for site effect if warranted.

